13.3 Accrual

The sample size will approximately range from 4-30 eligible patients in each disease, depending on the observance of DLTs and the number of dose levels tested. Based on the current practice, we anticipate that the accrual rate will be approximately 2-3 patients per month per disease.

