Study Objectives	 Primary Objectives To determine the maximum tolerated dose (MTD) of TGR-1202 when used in combination with ibrutinib in patients with relapsed or refractory CLL or MCL. To evaluate the safety and determine any dose limiting toxicities (DLTs) of TGR-1202 in combination with ibrutinib in patients with relapsed or refractory CLL or MCL. Secondary Objectives To preliminarily characterize the efficacy of TGR-1202 at its MTD in combination with ibrutinib by determining the overall response rate (ORR) defined as the sum of the complete response (CR) and partial response (PR) rate, as well as to determine the rate of nodal response with lymphocytosis (nPR), progression-free survival (PFS), and duration of response (DOR).

	Exploratory Objectives
	To assess whether apoptotic priming as determined by BH3 profiling and pharmacodynamic response as determined by phospho-flow are predictive of clinical response.
Efficacy Endpoints	 Efficacy Endpoints: Overall response rate, defined as sum of CR and PR rates. Responses will be determined according to response criteria as follows: MCL: International Working Group (Cheson et. al 2007; Revised Response Criteria for Malignant Lymphoma, [Appendix A]); CLL: International Workshop for Chronic Lymphocytic Leukemia (IW-CLL) Response Criteria (Hallek et al. 2008 [Appendix B]) as modified by Cheson et al., 2012.
Safety Endpoints	AEs will be evaluated during the treatment period and for 30 days following discontinuation from the study using CTCAE v4.0. The DLT observation period will be the first cycle (28 days).
	Up to 30 subjects per disease group (MCL and CLL/SLL), including a potential 12 qualified patients who will have completed the Phase Ib dose confirmation part of the study, may be enrolled. "Up to" is written because the Phase Ib can potentially stop early. Phase I Dose Confirmation:
	 3 + 3 design using Cycle 1 DLTs for both CLL/SLL and MCL patients, conducted independently in parallel, with a minimum of 3 patients in a cohort, as follows:
	 MCL: 3-6 patients at cohort 1 CLL/SLL: 3-6 patients at cohort 1
Study Design	• If no DLTs are reported among the initial in 3 patients in Cohort 1, the dose level will be considered safely cleared, and dose escalation may proceed to Cohort 2. If no DLTs are reported in 3 patients in Cohort 2, the dose will be considered safe for Cohort 3. If no DLT's are reported among the initial in 3 patients in Cohort 3, the Phase Ib part of the study will open.

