5.6.5 Replacement of Patients

Patients who discontinue treatment early due to disease progression or withdrawal will be asked to have all end-of-treatment safety evaluations performed as described in the protocol. If a patient withdraws from treatment during Cycle 1 due to any reason other than DLT and does not meet the minimum requirements for inclusion in the DLT-determining population described above, that patient will be replaced.

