13. STATISTICAL CONSIDERATIONS

This is a multi-center Phase I/Ib study evaluating the safety of the novel PI3k delta inhibitor TGR-1202 in combination with ibrutinib in patients with relapsed or refractory CLL or MCL. The primary endpoint of this study is to determine the maximum tolerated dose (MTD) in each disease group separately.

13.1 **Determining MTD**

This is a 3+3 design with four doses of TGR-1202 to be considered to determine MTD: 200mg (dose level -1), 400 mg (dose level 1, starting dose), 600 mg (dose level 2), and 800 mg (dose

level 3). Dose limiting toxicities (DLTs) were defined in section 5.6.3.

A cohort of 3 patients will enter at each dose level. If no DLT is seen in the first 3 eligible patients at dose level 1 or 2, a dose escalation will take place. If no DLT is seen in the first 3 eligible patients at dose level 3 or -1, 3 additional patients will be treated at that dose level. If 2 or more of the 3 eligible patients experience a DLT at dose level 1, 2, or 3, the next cohort of 3 patients will be treated at the next lower dose level, unless 6 patients have already been treated at that dose level. If 2 or more of the first 3 eligible patients experience a DLT at dose level -1, the study will be terminated early. If 1 of the first 3 patients experiences a DLT then 3 additional patients will be treated at that dose level. If there is no DLT in the 3 additional patients then dose escalation will take place. If this is dose level 3 or -1, then this dose is the MTD. If 1 or more of the 3 additional patients experience(s) DLT then the MTD is considered exceeded, and 3 more patients are treated at the next lower dose, unless 6 patients have already been treated at that dose level. If this is dose level -1, the study will be terminated early.

A minimum of six patients must be evaluated at the highest tolerated dose level, and fewer than 2 patients in 6 should experience DLT.

Table 5 shows the probability of escalation under various true DLT rates. With this design, there is 91% probability of dose escalation if the true rate of DLT is 10% and 17% probability of escalation if the true DLT rate is 50%.

Table 5: probability of dose escalation

True Rate of DLT	Prob. of Escalation
10%	0.91
20%	0.71
30%	0.49
40%	0.31
50%	0.17
60%	0.08

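### The stated upper size of 30 per disease matches the synopsis escalation rule, not Sections 13.1 and 13.2, which allow 36 before replacements (minor correction)

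*Combined protocol and SAP*

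**What the plan says.** Section 13.3 (Accrual): "The sample size will approximately range from 4-30 eligible patients in each disease". It adds that the size depends on the DLTs observed and on how many levels are tested. The synopsis (Study Design) opens with "Up to 30 subjects per disease group (MCL and CLL/SLL" and explains the upper-limit wording by the possibility of stopping early.

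Section 13.1 sets the escalation rules:
- There are "four doses of TGR-1202 to be considered to determine MTD": levels -1, 1, 2 and 3, starting at level 1.
- "A cohort of 3 patients will enter at each dose level".
- "If 1 of the first 3 patients experiences a DLT then 3 additional patients will be treated at that dose level".
- "If no DLT is seen in the first 3 eligible patients at dose level 3 or -1, 3 additional patients will be treated" there.
- After two or more DLTs in three, "the next cohort of 3 patients will be treated at the next lower dose level, unless 6 patients have already been treated" there. The same step-down follows one DLT in the first three plus at least one in the next three.
- The highest tolerated level needs six patients with fewer than two DLTs. Level -1 can be the maximum tolerated dose (MTD).

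Section 13.2 adds 12 patients at the MTD. Section 5.6.5 says of a patient who leaves in Cycle 1 without a DLT and is not evaluable for DLT: "that patient will be replaced".

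The synopsis has a different step-down rule. After two or more DLTs in Cohort 2 or 3, the next dose that has already cleared becomes the Phase Ib dose, and no further patients are described at that level.

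**The concern.** The upper figure in Section 13.3 should follow from the rules two subsections earlier, and it does not. Section 13.1 back-fills a level that holds only three patients and, if the back-fill also fails, steps down again. All four levels can then reach six patients. No section says what gives way if Phase I passes 18: the figure of 30 or the 12 Phase Ib patients. Nor does any section say whether replaced patients count towards 30. At stake are an enrolment figure that sites and oversight bodies will read as a limit, and the clarity of the Phase Ib size on which the Section 13.2 precision is based.

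**Working it through.** **1. The plan's own figures.**

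- Upper end: 3 levels × 6 + 12 = 30. This is the maximum under the synopsis rule, where Phase I stops at 18.
- Lower end: two DLTs in the first two patients at level 1, and again at level -1, gives 2 + 2 = 4. It is explicable and not an error.
- Table 5: the probability of escalating is (1−p)³ + 3p(1−p)⁵. At p = 0.10 this is 0.729 + 0.177 = 0.906; at p = 0.30 it is 0.343 + 0.151 = 0.494. Both match Table 5 (0.91, 0.49), so the per-level rule is read as the plan intends.

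**2. Longest path under Section 13.1.**

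| Step | Level | DLTs | Treated at level | Phase I total |
|---|---|---|---|---|
| 1 | 1 | 0/3 | 3 | 3 |
| 2 | 2 | 0/3 | 3 | 6 |
| 3 | 3 | 0/3, then ≥2/3 (or 1/3, then ≥1/3) | 6 | 12 |
| 4 | 2 (back-fill) | ≥2/3 | 6 | 15 |
| 5 | 1 (back-fill) | ≥2/3 | 6 | 18 |
| 6 | -1 | ≤1/6, so MTD | 6 | 24 |

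Phase I = 4 × 6 = 24. With Phase Ib, 24 + 12 = **36**, which is 6/30 = 20% above the stated figure. If level 3 fails in its first three patients, the totals are 21 and 33. Enumerating all paths shows that 33 and 36 are the only totals above 30.

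**3. How likely this is, before replacements.** Worked case, assuming a DLT rate of 0.30 at every level:

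- 0/3: 0.7³ = 0.343. At least 2/3: 0.216.
- Level 3 fails with six treated: 0.343 × 0.216 + 0.441 × 0.657 = 0.364.
- Level -1 clears with six: 0.343 × (0.343 + 0.441) + 0.441 × 0.343 = 0.420.
- Total 36: 0.343² × 0.364 × 0.216² × 0.420 = 0.00084.
- Total 33: 0.343² × 0.216 × 0.216² × 0.420 = 0.00050.
- Sum: 0.0013, or 0.13%.

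Other assumed profiles:

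| DLT rate at levels -1/1/2/3 | P(total > 30) | Expected total |
|---|---|---|
| 10% at all | 0.004% | 24.8 |
| 20% at all | 0.06% | 23.3 |
| 30% at all | 0.13% | 19.7 |
| 40% at all | 0.10% | 15.6 |
| 5/10/20/30% | 0.06% | 25.0 |
| 10/20/30/40% | 0.27% | 23.8 |
| 10/30/40/50% | 0.44% | 22.8 |

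The largest value on a grid of non-decreasing profiles (steps of 0.1) is 0.58%.

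**4. Replacements.** A path with 18 evaluable Phase I patients and an MTD already totals 18 + 12 = 30, so one replaced patient makes 31. At 30% at all levels its probability is 0.0090 + 0.0113 + 0.0231 + 0.0096 = 0.053. It is about 4% to 8% over flat rates of 10% to 30% and the rising profiles, and lower at a flat 40%. The documents give no replacement rate. Over the same profiles, P(more than 30 enrolled) is about 3% to 5% if 5% of Phase I patients are replaced, 5% to 10% if 10% are, and 7% to 17% if 15% are. These three rates are assumptions.

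**5. If 30 were a hard cap.** On the 24-patient path Phase Ib would be 30 − 24 = 6; on the 21-patient path, 9. The normal-approximation 90% half-width at a rate of 0.5 is 1.645 × √(0.25/n). It is 0.237 at n = 12, consistent with the ±25% in Section 13.2, and 0.336 at n = 6.

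**The case against.** Section 13.3 says the size is approximate and gives it as a planning range under Accrual. The paths above 30 are very improbable, and no power, precision or analysis figure in the plan is computed from 30. All of that stands, and it is why the point is minor. It does not remove the inconsistency: the synopsis words 30 as an upper limit and explains only why enrolment might fall short of it.

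The chain of successive back-fills is not written out in Section 13.1; it comes from reapplying the cohort rule. Section 5.2.3 also speaks of a single escalation or de-escalation. If that excludes consecutive step-downs, Phase I again stops at 18. This also stands. The documents hold competing rules, and 36 is the maximum only if Section 13.1 governs as worded.

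A reader might infer that Phase Ib will be cut to six and the Section 13.2 precision lost. The documents do not support that. Section 13.2 says the 12 will be treated, and no section makes them yield to a cap. Nor should an exact limit for six patients (up to 42 points above the estimate) be set against the ±25%, which is a normal approximation for 12. The like-for-like pairs are 34 against 24 points (normal) or 42 against 28 (exact).

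**Conclusion.** The point holds as a minor correction. The stated upper size of 30 is not the maximum of Sections 13.1 and 13.2, which is 24 + 12 = 36 per disease before replacements; 30 belongs to the synopsis rule. A reader might conclude that the trial is likely to overrun. It is not. By this route the probability is below about 0.6% in all profiles tried, and expected enrolment is about 20 to 25 in the flat profiles up to 30% and the rising ones. Replacements are the more plausible way past 30, but how often depends on a rate that the documents do not give. The maximum of 36 rests on the wording of Section 13.1 alone; the probabilities rest on assumed DLT rates and independent patients. Determination of the MTD is not affected.

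**What to change.** 1. Reconcile the escalation rules in the synopsis with Sections 5.2.3 and 13.1. Which rule governs is for the sponsor to settle.
2. Restate the upper size in Section 13.3 and the synopsis as the maximum of that rule: 36 (24 + 12) if Section 13.1 governs, 30 (18 + 12) if the synopsis rule does.
3. State that patients replaced under Section 5.6.5 are in addition to that number.
4. State that the 12 Phase Ib patients are kept whatever the size of Phase I. If 30 is meant as a hard cap, say so and restate the Section 13.2 precision for the smaller Phase Ib (about 34 points at n = 6 against 24 at n = 12, normal approximation).

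Once the rule is settled, the cost is wording in Section 13.3 and the synopsis. Restating the size and how replacements count does not change expected enrolment.

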13.4 Analysis Plan for Secondary Objectives

Phase I/Ib Study of TGR-1202 plus Ibrutinib in Patients with Select B-Cell Malignancies Version Date: 10.23.2019

The secondary objectives include assessment of the overall response rate, nodal partial response rate, progression-free survival, and duration of response. Due to the exploratory nature, the analysis for secondary endpoints will largely be descriptive. Response rate and duration of response will be summarized descriptively and the Kaplan Meier method will be used to estimate the median progression-free survival time and progression-free survival. A similar descriptive analysis will be performed for laboratory correlative studies of BH3 profiling and pharmacodynamic markers such as phosphorylated levels of AKT, BTK, and ERK, as well as Ki-67 level. If feasible, association between clinical response and laboratory endpoints will be explored.

14. PUBLICATION PLAN

The results should be made public within 24 months of reaching the end of the study. The end of the study is the time point at which the last data items are to be reported, or after the outcome data are sufficiently mature for analysis, as defined in the section on Sample Size, Accrual Rate and Study Duration. If a report is planned to be published in a peer-reviewed journal, then that initial release may be an abstract that meets the requirements of the International Committee of Medical Journal Editors. A full report of the outcomes should be made public no later than three (3) years after the end of the study.

	It is recognized that in Waldeyer's ring or extranodal sites with high physiologic uptake or with activation within spleen or marrow (eg, with chemotherapy or myeloid colony-stimulating factors), uptake may be greater than normal mediastinum and/or liver. In this circumstance, complete metabolic response may be inferred if uptake at sites of initial involvement is no greater than surrounding normal tissue even if the tissue has high physiologic uptake	No extralymphatic sites of disease
Nonmeasured lesion	Not applicable	Absent
Organ enlargement	Not applicable	Regress to normal
New lesions	None	None
Bone marrow	No evidence of FDG-avid disease in marrow	Normal by morphology; if indeterminate, IHC negative
Partial	Partial metabolic response	Partial remission (all of the following)
Lymph nodes and extralymphatic sites	Score 4 or 5 [†] with reduced uptake compared with baseline and residual mass(es) of any size	≥ 50% decrease in SPD of up to 6 target measurable nodes and extranodal sites
	At interim, these findings suggest responding disease	When a lesion is too small to measure on CT, assign 5 mm × 5 mm as the default value
	At end of treatment, these findings indicate residual disease	When no longer visible, 0×0 mm

Response and Site	PET-CT-Based Response	CT-Based Response
		For a node > 5 mm × 5 mm, but smaller than normal, use actual measurement for calculation
Nonmeasured lesions	Not applicable	Absent/normal, regressed, but no increase
Organ enlargement	Not applicable	Spleen must have regressed by > 50% in length beyond normal
New lesions	None	None
Bone marrow	Residual uptake higher than uptake in normal marrow but reduced compared with baseline (diffuse uptake compatible with reactive changes from chemotherapy allowed). If there are persistent focal changes in the marrow in the context of a nodal response, consideration should be given to further evaluation with MRI or biopsy or an interval scan	Not applicable
No response or stable disease	No metabolic response	Stable disease
Target nodes/nodal masses, extranodal lesions	Score 4 or 5 with no significant change in FDG uptake from baseline at interim or end of treatment	< 50% decrease from baseline in SPD of up to 6 dominant, measurable nodes and extranodal sites; no criteria for progressive disease are met
Nonmeasured lesions	Not applicable	No increase consistent with progression
Organ enlargement	Not applicable	No increase consistent with progression
New lesions	None	None
Bone marrow	No change from baseline	Not applicable
Progressive disease	Progressive metabolic disease	Progressive disease requires at least 1 of the following
Individual target nodes/nodal masses	Score 4 or 5 with an increase in intensity of uptake from baseline and/or	PPD progression:
Extranodal lesions	New FDG-avid foci consistent with lymphoma at interim or end-of-treatment assessment	An individual node/lesion must be abnormal with: LDi > 1.5 cm and Increase by $\ge 50\%$ from PPD nadir and

Version Date: 10.23.2019

Response and Site	PET-CT-Based Response	CT-Based Response
		An increase in LDi or SDi from nadir 0.5 cm for lesions ≤ 2 cm 1.0 cm for lesions > 2 cm In the setting of splenomegaly, the splenic length must increase by > 50% of the extent of its prior increase beyond baseline (eg, a 15-cm spleen must increase to > 16 cm). If no prior splenomegaly, must increase by at least 2 cm from baseline New or recurrent splenomegaly
Nonmeasured lesions	None	New or clear progression of preexisting nonmeasured lesions
New lesions	New FDG-avid foci consistent with lymphoma rather than another etiology (eg, infection, inflammation). If uncertain regarding etiology of new lesions, biopsy or interval scan may be considered	Regrowth of previously resolved lesions A new node > 1.5 cm in any axis A new extranodal site > 1.0 cm in any axis; if < 1.0 cm in any axis, its presence must be unequivocal and must be attributable to lymphoma Assessable disease of any size unequivocally attributable to lymphoma
Bone marrow	New or recurrent FDG-avid foci	New or recurrent involvement

- Abbreviations: 5PS, 5-point scale; CT, computed tomography; FDG, fluorodeoxyglucose; IHC, immunohistochemistry; LDi, longest transverse diameter of a lesion; MRI, magnetic resonance imaging; PET, positron emission tomography; PPD, cross product of the LDi and perpendicular diameter; SDi, shortest axis perpendicular to the LDi; SPD, sum of the product of the perpendicular diameters for multiple lesions.
- 🖃 * A score of 3 in many patients indicates a good prognosis with standard treatment, especially if at the time of an interim scan. However, in trials involving PET where de-escalation is investigated, it may be preferable to consider a score of 3 as inadequate response (to avoid undertreatment). Measured dominant lesions: Up to six of the largest dominant nodes, nodal masses, and extranodal lesions selected to be clearly measurable in two diameters. Nodes should preferably be from disparate regions of the body and should include, where applicable, mediastinal and retroperitoneal areas. Non-nodal lesions include those in solid organs (eg, liver, spleen, kidneys, lungs), GI involvement, cutaneous lesions, or those noted on palpation. Nonmeasured lesions: Any disease not selected as measured, dominant disease and truly assessable disease should be considered not measured. These sites include any nodes, nodal masses, and extranodal sites not selected as dominant or measurable or that do not

meet the requirements for measurability but are still considered abnormal, as well as truly assessable disease, which is any site of suspected disease that would be difficult to follow quantitatively with measurement, including pleural effusions, ascites, bone lesions, leptomeningeal disease, abdominal masses, and other lesions that cannot be confirmed and followed by imaging. In Waldeyer's ring or in extranodal sites (eg, GI tract, liver, bone marrow), FDG uptake may be greater than in the mediastinum with complete metabolic response, but should be no higher than surrounding normal physiologic uptake (eg, with marrow activation as a result of chemotherapy or myeloid growth factors).

•  PET 5PS: 1, no uptake above background; 2, uptake ≤ mediastinum; 3, uptake > mediastinum but ≤ liver; 4, uptake moderately > liver; 5, uptake markedly higher than liver and/or new lesions; X, new areas of uptake unlikely to be related to lymphoma.

APPENDIX B CHRONIC LYMPHOCYTIC LEUKEMIA RESPONSE DEFINITION (HALLEK ET AL. 2008)

Assessment of response should include a careful physical examination and evaluation of the blood and marrow.

CR requires all of the following criteria as assessed at least 2 months after completion of therapy:

- 1. Peripheral blood lymphocytes (evaluated by blood and differential count) below $4 \times 10^9 / L (4000 / \mu L)$.
- 2. Absence of significant lymphadenopathy (e.g., lymph nodes >1.5 cm in diameter) by physical examination.
- 3. No hepatomegaly or splenomegaly by physical examination and CT.
- 4. Absence of constitutional symptoms.
- 5. Blood counts above the following values:
 - Neutrophils >1.5 x $10^9/L$ ($1500/\mu L$) without need for exogenous growth factors.
 - Platelets >100 x 10^9 /L (100 000/ μ L) without need for exogenous growth factors.
 - Hemoglobin >110 g/L (11.0 g/dL) without red blood cell transfusion or need for exogenous erythropoietin.

For patients in clinical trials, a marrow aspirate and biopsy should be performed at least 2 months after the last treatment and if clinical and laboratory results listed above a-e demonstrate that a CR has been achieved. To define a CR, the marrow sample must be at least normocellular for age, with less than 30% of nucleated cells being lymphocytes. Lymphoid nodules should be absent. In some cases, lymphoid nodules can be found, which often reflect residual disease. These nodules should be recorded as "nodular PR." Moreover, immunohistochemistry should be performed to define whether these nodules are composed primarily of T cells or lymphocytes other than CLL cells or of CLL cells. If the marrow is hypocellular, a repeat determination should be performed after 4 weeks, or until peripheral blood counts have recovered. However, this time interval should not exceed 6 months after the last treatment. A marrow biopsy should be compared with that of pretreatment marrow. In general practice, the use of a marrow biopsy for evaluating a CR is at the discretion of the physician.

In clinical trials aiming at maximizing the CR rate, the quality of the CR should be assessed for MRD by flow cytometry or by immunohistochemistry.

A controversial issue is how best to categorize the response of patients who fulfill all the criteria for a CR (including the marrow examinations described above) but who have a persistent anemia or thrombocytopenia or neutropenia apparently unrelated to CLL but related to drug toxicity. We recommend that these patients be considered as a different category of remission: CR with incomplete marrow recovery (CRi). For the definition of this category, CRi, the marrow evaluation (described above) should be performed with scrutiny and not show any clonal infiltrate. In clinical trials, CRi patients should be monitored prospectively to determine whether their outcome differs from that of patients with detectable residual or with noncytopenic CR.

Partial Response: (PR)

To define a PR (partial remission): at least two of the criteria of Group A plus one of the criteria of Group B have to be met. The parameters below should be documented for no less than 2 months. Constitutional symptoms persisting for >1 month should be recorded.

Group A

- a. Decrease in the number of blood lymphocytes by 50% or more from the value before therapy.
- b. Reduction in lymphadenopathy (by PE and CT scans) as defined by the following:
 - A decrease in lymph node size by 50% or more either in the sum products of up to 6 lymph nodes, or in the largest diameter of the enlarged lymph node(s) detected prior to therapy.
 - No increase in any lymph node, and no new enlarged lymph node. In small lymph nodes (<2 cm), an increase of less than 25% is not considered to be significant.
- c. Reduction in the noted pretreatment enlargement of the spleen or liver by 50% or more, as detected by CT scan.

Group B

- d. Blood count should show one of the following:
 - Neutrophils >1.5 x $10^9/L$ ($1500/\mu L$) without need for exogenous growth factors.
 - Platelet count >100 x 10⁹/L (100 000/μL) or 50% improvement over baseline without need for exogenous growth factors.
 - Hemoglobin >110 g/L (11.0 g/dL), or 50% improvement over baseline without requiring red blood cell transfusions or exogenous erythropoietin.

Chronic Lymphocytic Leukemia Response Definition (Hallek et al. 2008) (continued)

Progressive	Progressive disease during or after therapy is characterized by at least one of the	
Disease:	following:	
(PD)	 a. Lymphadenopathy: Progression of lymphadenopathy is often discovered by physical examination and should be recorded. In CLL, the use of CT scans usually does not add much information for the detection of progression or relapse. Therefore, the use of imaging methods to follow CLL progression is at the discretion of the treating physician. Disease progression occurs if one of the following events is observed: • Appearance of any new lesion, such as enlarged lymph nodes (>1.5 cm), splenomegaly, hepatomegaly, or other organ infiltrates. • An increase by 50% or more in greatest determined diameter of any previous site. b. An increase in the previously noted enlargement of the liver or spleen by 50% or more, or the de novo appearance of hepatomegaly or splenomegaly. c. An increase in the number of blood lymphocytes by 50% or more, with at least 5000 B-lymphocytes per μL. d. Transformation to a more aggressive histology (e.g., Richter syndrome). Whenever possible, this diagnosis should be established by lymph node biopsy. e. Occurrence of cytopenia (neutropenia, anemia, or thrombocytopenia) attributable to CLL • During therapy: Cytopenias may occur as a side effect of many therapies. During therapy, cytopenias cannot be used to define disease progression. • After treatment: The progression of any cytopenia (unrelated to autoimmune cytopenia), as documented by a decrease of Hb levels by >20 g/L (2 g/dL) or to <100 g/L (10 g/dL), or by a decrease of platelet counts by >50% or to <100 x 10°/L (100,000/μL), which occurs at least 3 months after treatment, defines disease progression, if the marrow biopsy demonstrates an infiltrate of clonal CLL cells. 	
Stable	Patients who have not achieved a CR, PR, or nPR and who have not exhibited	
Disease:	progressive disease, will be considered to have stable disease (which is equivalent	
(SD)	to a non-response).	
Nodular	As per Cheson et al., 2012, patients who achieve a radiographic PR but continue to	
Partial	have a lymphocytosis with $>5,000$ B-lymphocytes per μL are considered to have a	
Response	nodular partial response, also known as PR with lymphocytosis, due to the fact that	
(nPR)	they appear to derive a similar clinical benefit from BCR inhibitors as patients who achieve a traditional PR.	

Phase I/Ib Study of TGR-1202 plus Ibrutinib in Patients with Select B-Cell Malignancies Version Date: 10.23.2019

